1.2 Abbreviations

Abbreviation Definition of Term

| | |
|----------------|------------------------------------------------------------------|
| AE | Adverse event |
| ANZGOG | Australia New Zealand Gynaecological Oncology Group |
| ASAR | Australian Sonographers Accreditation Registry |
| BIS | Bioimpedance Spectroscopy |
| BMI | Body Mass Index |
| CDMU | Central Data Management Unit |
| CI | Chief Investigator |
| CRF | Case Report Form |
| CT | Computed Tomography |
| CTCAE | Common Terminology Criteria for Adverse Events |
| ECOG | Eastern Cooperative Oncology Group |
| eCRF | Electronic Case Report Form |
| EDTA | Ethylenediamine Tetraacetic Acid |
| ESMO | European Society for Medical Oncology |
| EV | Extracellular Vesicles |
| FACT | Functional Assessment of Cancer Therapy |
| FBC | Full Blood Count |
| FoR | Fear of Recurrence |
| HREC | Human Research Ethics Committee |
| HRQL | Health Related Quality of Life |
| ICH-GCP | International Council for Harmonisation - Good Clinical Practice |
| IDSMC | Independent Data Safety Monitoring Committee |
| IFL | Inguino-Femoral Lymphadenectomy |
| IGCS | International Gynaecological Cancer Society |
| LFT | Liver Function Tests |
| LND | Lymph Node Dissection |
| MRI | Magnetic Resonance Imaging |
| NPV | Negative Predictive Value |
| PCR | Polymerase Chain Reaction |
| PET | Positron Emission Tomography |
| PI | Principal Investigator |
| PROMS | Patient Reported Outcomes |
| PM | Project Manager |
| PPV | Positive Predictive Values |
| QCGC | Queensland Centre for Gynaecological Cancer |
| QALY | Quality Adjusted Life Year |
| QLD | Queensland |
| QoL | Quality of Life |
| SAE | Serious Adverse Event |
| SCC | Squamous Cell Carcinoma |
| SNB | Sentinel Node Biopsy |
| SGO | Society of Gynaecologic Oncology |
| TMC | Trial Management Committee |
| UQ | University of Queensland |
| US | Ultrasound |
| USM | Ultrasound Monitoring |
| UQRDM | The University of Queensland Research Data Manager |

1.3 Trial Schema

[figure not shown]

Figure 1. Trial Schema

2. Justification of the ANVU Trial

Treatment of vulvar cancer causes significant morbidity. Despite being a rare cancer at least 2500 survivors of vulvar cancer live in Australia [2]. Most survivors must live with the detrimental, life-long impacts resulting from their cancer treatment because there are currently no alternatives to mitigate these impacts. The personal and societal burden this entails is significant. To control such cancer-associated burden is a national priority [3].

Clinical palpation of the groin region and medical imaging scans do not reliably detect groin node involvement [4, 5]. Hence, current clinical guidelines recommend all women diagnosed at apparent Stage 1 or 2 have a surgical groin LND [6]. This can be performed as a full IFL to remove all groin nodes,

or as SNB to remove selected (one or two) nodes [7-9]. SNB is less invasive, however, is appropriate only for vulvar cancers <4cm in diameter and unifocal tumours (~50% of all Stage 1 and 2 vulvar cancers) [4, 8, 9]. SNB is also associated with a false negative rate (10%) that increases the risk of undetected nodes [4, 7]. While groin LND is often curative, most survivors will report debilitating and long-term side effects including persistently painful and disfiguring limb swelling, impaired mobility and increased susceptibility to infections [10-13] [7, 14-16]. Strategies to prevent these side effects without compromising survival are lacking and are the focus of this clinical trial.

In 20% of cases (~80 Australian women per year), groin LND will reveal positive nodes (i.e., metastases) [8, 9], which triggers a referral for radiation treatment. If positive groin nodes are missed, and over time become enlarged, clinically palpable and attached to the overlying skin, >90% of women will die within 12 months despite subsequent treatment [4, 5]. Conversely, if groin node involvement is detected early (e.g., by ultrasound) while still small, survival outcomes are excellent [10]. Ultrasound technology is potentially as accurate as LND due to recent advances in resolution and technologies such as 2D/3D volumetric assessments and tissue flow. Furthermore, ultrasound is superior to magnetic resonance imaging (MRI), and to standard computed tomography (CT) and positron emission tomography (PET) scans in capturing groin node involvement because it has a higher resolution, avoids harmful radiation, and the technology is readily accessible outside of high-volume metropolitan areas [11].

We propose to reduce surgical morbidity by replacing upfront groin LND for vulvar cancer patients with serial high-resolution ultrasound to detect groin metastases. Groin LND will only be required for the few women with ultrasound-detected metastasis when they are still small. The ANVU trial will determine the value of serial groin ultrasound examinations in stage 1 and 2 vulvar cancer patients and whether it is feasible and safe to de-escalate the extent of vulvar cancer surgery to achieve improved outcomes for affected patients.

3. Introduction

3.1 Background

Vulvar cancer is a rare disease that, by its intimate nature, is also largely hidden from public discourse. With an incidence of 2.5/100,000, approximately 400 Australian women are diagnosed every year [2, 4, 5]. Standard treatment of invasive vulvar cancer comprises of surgical removal of the primary tumour plus surgical groin LND [4, 5, 12]. Groin LND can be delivered through a full Inguino Femoral Lymph Node Dissection (IFL) (removing as many nodes as possible) or through a Sentinel Node Biopsy (SNB) (removing only one or two targeted groin lymph nodes). While the gold standard is often curative, groin LND is associated with debilitating short and long-term morbidity for virtually all women requiring this procedure (see 3.3 below) [13-19].

Adverse outcomes range from painful and disfiguring limb swelling, compromised function, impaired mobility, and greater susceptibility to infection. Sparing women a groin LND could greatly reduce the incidence and burden of these problems, improve recovery time, and facilitate their return to normal daily activities [2, 7]. It is not possible at present to offer treatment that lessens morbidity without exposing affected patients to the risks of impaired survival.

Australian women with this rare cancer bear an unacceptably high (and potentially avoidable) treatment-related burden. This clinical trial (ANVU) is the first step to address this problem in a novel yet pragmatic way. The overall outcome of ANVU is a novel, less invasive alternative to vulvar cancer LND associated with significantly less morbidity, without compromising survival.

3.2 Importance of Groin Nodes

Vulvar cancer develops from vulvar skin. It can spread locally to adjacent structures (vagina, urethra, anus) or via lymphatic channels to regional lymph nodes in the groin [2, 5]. If groin nodes are involved, the cancer is upgraded to Stage 3. This indicates a worse prognosis compared to tumours confined to local involvement [4]. Patients with groin node metastasis require further treatment. Unfortunately pre-treatment detection via groin clinical examination (palpation) and medical imaging scans do not reliably detect microscopic groin node involvement [2, 5]. Hence current clinical guidelines mandate that all patients (except those with Stage 1A disease) require surgical groin LND to mitigate the risk of missing groin node metastases [12]. In 30% of cases (~120 Australian women per year) a groin LND reveals positive (involved) nodes [8, 9], and a concomitant need for postoperative radiation treatment. Should positive groin nodes be missed and become enlarged and clinically palpable, more than 90% of patients will die within 12 months despite subsequent treatment [2, 5]. Conversely, if groin node involvement is detected early while still small, survival outcomes are expected to be excellent. For those reasons, the detection of clinically palpable, enlarged groin nodes is an appropriate marker for oncological safety in vulvar cancer (primary outcome of this clinical trial).

3.3 Outcomes of Groin Lymph Node Dissection

While effective, groin LND inevitably leads to substantial short- and long-term morbidity [2, 5]. Groin LND can be performed as an IFL; removing all groin nodes or SNB to remove selected (one or two) nodes [7-9]. For SNB and IFL, respectively, adverse outcomes include rates of wound breakdown in 11.7% vs 34%; cellulitis 4.5% vs 21.3%; and life-long swelling of the legs (lymphoedema) in 60% of patients [7-9]. The incidence of surgery-related morbidity is higher in patients who undergo IFL [7]. Less invasive SNB, however, is appropriate in only 50% of cases. SNB is also associated with a false negative rate (up to 10%) that increases the risk of undetected nodes (1% vs. 5%) [4, 7]. For the ~70% to 80% of patients who have negative groin nodes (i.e., no cancer within the nodes), groin LND has no clinical benefit and patients still suffer from the potential adverse outcomes of undergoing this procedure.

3.4 Preliminary Data

Our comprehensive literature review focussed on the five critical areas of the proposed ANVU study:

Surgical morbidity: Our comprehensive review of 35 studies found >50% of women developed one or more complications from groin LND [18]. A prospective, longitudinal gynaecological cancer cohort study (n=546, funded by Cancer Australia APP519711) [15] undertaken by team members supported this, finding that 91% of women with vulvar cancer either self-reported lower limb swelling (45%) without a formal diagnosis; 25% received a formal clinical diagnosis of lymphoedema; and a further 41% reported both. Other common adverse outcomes included long length of hospital stay (8-13 days), wound breakdown (12%-34%), and cellulitis (5%-21%) [7, 9, 13].

Quality of life (QoL): Andersen and [name]'s (1983) earliest work flagged that women who had experienced vulvar surgery registered emotional distress in the 88th percentile [20] as a result of these morbidities. We subsequently assessed the more detailed QoL impact of vulvar cancer in a mixed-method program that developed a reliable and valid vulvar-cancer specific QoL subscale to accompany the Functional Assessment of Cancer Therapy (FACT) [15-17, 19, 21]. In this study, women reported substantial reductions in emotional, physical and social functioning, activities of daily living, as well as sexual wellbeing and perceptions of body image associated with standard vulvar cancer treatment [14]. Return to work was often impaired [17]. In a complementary qualitative study of QoL after treatment, we found that women with lymphoedema or iatrogenic leg pain reported significantly worse (5-30% worse) QoL in the social, physical and sexual domains than women who did not report these problems [22]. This study identified four main themes: fear, body image concerns, altered sexuality and lymphoedema, with the most detrimental impact reported by women who experienced radical vulvar excision, multiple vulvar procedures and/or who developed lymphoedema [14].

Our pilot data confirm that groin ultrasound is a clinically feasible alternative to LND [17]. Cls [name] and [name] undertook a pilot study to determine whether 3-monthly groin USM could be performed in lieu of upfront groin LND after a negative bilateral groin ultrasound in 32 women with apparent Stage 1 or 2 vulvar cancer. Three positive nodes (9.4%) were detected during a median

follow-up of 37 months (none lost to follow-up) and 29 patients could be spared a groin LND. All ultrasound-detected positive nodes developed within 12 months. One participant died of her groin recurrence (3.1%). The sensitivity of serial groin USM was 100% (95% CI: 44-100%), with specificity of 97% (95% CI: 83-99%) and negative predictive value of 100% (95% CI: 88-100%). These compelling pilot data justify a larger study on serial groin ultrasound in lieu of upfront groin LND in selected patients with vulvar cancer. In this study sensitivity of the monitoring via 2-monthly ultrasonography was calculated as the proportion of true-positive ultrasonic scans (confirmed histologically) of the total number of true-positive and false-negative scans. Similarly, the specificity was calculated as the proportion of true-negative scans of the total number of true-negative and false-positive scans. A false-positive scan was determined after fine needle cytology was negative; two nodes were surgically removed and found to be negative histologically.

Standardisation of groin ultrasound is achievable. Encouraged by our pilot study, CIA [name] recently completed a prospective feasibility study of synoptic reporting of groin ultrasound findings in women with vulvar cancer (pre-ANVU study, ACTRN12622000886785; publication in preparation). It applied 10 rigorous criteria for groin node ultrasound. Eligible women underwent groin ultrasound prior to planned groin LND. All 20 women had all 10 criteria reported. This successful feasibility and quality assurance study warrants using those 10 criteria in our ANVU trial. Furthermore, the pre-ANVU study attracted the award of the Australian Society of Gynaecological Oncologists Tony McCartney Surgical Innovation prize in 2023, citing the work represents the “perfect synthesis of reducing significant morbidity associated with vulvar cancer surgery ... that enables de-escalation of vulvar cancer surgery [that is] safe for patients”.

4. Expected Outcomes and Health Impact

This randomised clinical trial will evaluate bilateral groin ultrasound to predict groin lymph node involvement in vulvar cancer patients. The knowledge embodied in the project outcome is a first step towards facilitating a change in current clinical practice towards equally safe but less invasive management of vulvar cancer with superior outcomes for women.

Consistent with the objectives of our study, outcomes include:

1. Information on post-intervention quality of life and function that is crucial for women’s and clinicians’ decision-making.
2. Affirmation of the safety of serial high-resolution groin USM of patients randomised to serial groin USM versus groin LND.
3. Affirmation of the diagnostic accuracy of high-resolution ultrasound to predict groin lymph node involvement in vulvar cancer patients.
4. Optimising patient outcomes and minimise the incidence of morbidity and costs associated with groin LND, by providing a thorough evaluation of how current surgical practice can be improved.
5. Early data on the utility of novel blood and tissue biomarkers for vulvar cancer, similar to those available for ovarian, bowel and other cancers.

The critical knowledge embodied in project outcomes is the first step towards translation into clinical practice. The findings will enable the stakeholders to weigh the benefits more accurately versus risks

of each procedure in terms of prognostic sensitivity, safety, surgical recovery, pain, length of hospital stay, quality of life and function.

If groin USM is demonstrated to be feasible and safe, the ANVU trial will also have an impact on improving the quality of care for Australian and international vulval cancer patients by providing high quality evidence to support shared decision-making which is a central component of patient-centred care. Shared decision-making involves describing alternative options for care and providing patients with the best available evidence about the benefits, harms, and uncertainty for each option and supporting patients to consider their values and preferences to achieve an informed decision.

The ANVU trial will also provide Australian and international vulvar cancer patients with the opportunity to benefit from innovative medical research—this is the only clinical intervention trial to focus on the minimisation of iatrogenic harm in this under-researched group.

Post-trial options: If the trial demonstrates feasibility and safety of groin USM, there are several options of continuing towards clinical practice management change:

- Continue enrolment into the ANVU trial as a phase 3 randomised clinical trial to reach 790 patients with a 4-year survival primary endpoint.
- Continue enrolment into the ANVU trial with an unspecified number of patients and observe survival outcomes.
- Monitor survival outcomes of the 240 enrolled patients for 4 years.
- Perform a phase 4 non-randomised, observational study on serial groin ultrasound.
- Develop a subsequent phase 2/3 randomised controlled trial with molecular biomarkers for stratification.
- Co-develop a decision-making tool with consumer representatives and other stakeholders to provide patients with information on the probabilities of important outcomes associated with groin USM and LND, and related uncertainty, based on trial primary and key secondary endpoints, and uncertainty, in a format to elicit patients' values and preferences to support shared decision-making.

5. Trial Design

5.1 Primary Research Question

Is incidence of groin metastases (defined as enlarged, clinically palpable, fixed to skin and histologically positive nodes) comparable between women randomised to serial groin USM or upfront groin LND?

5.2 Aim

To determine whether groin USM (1) is effective and safe to replace invasive groin LND to manage vulvar cancer; (2) decreases the morbidity associated with vulvar cancer surgery; and (3) is cost effective.

5.3 Primary Objective

Determine the incidence of palpable, fixed to skin and histologically positive groin nodes in women with vulvar cancer randomised to serial high-resolution groin USM compared to standard upfront surgical groin LND at 12 months.

5.4 Secondary Objective

1. Compare Patient Reported Outcomes (PROMs) and Health Related Quality of Life (HRQL) between the groups
2. Compare pain and adverse events (AEs) (morbidity) between the groups
3. Compare incidence of lower limb lymphoedema at 12 months post-surgery between the groups
4. Compare cost and cost effectiveness between all groups
5. To assess the role of molecular biomarkers to accurately determine the burden of disease (positive lymph nodes) in vulvar cancer, assist with risk stratification and aid disease surveillance
6. Determine the diagnostic accuracy of pre-operative, standardised high-resolution groin ultrasound to identify groin node metastasis.

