| Study Objectives | 
Primary objective:
 
 To determine the incidence of palpable, fixed to skin and histologically positive groin nodes at 12 months in women with vulvar cancer randomised to serial high-resolution groin USM versus standard surgical groin LND 
Secondary objectives:
 
 Compare Patient Reported Outcomes (PROMS) and Health-Related Quality of Life (HRQL) between the groups Compare pain and adverse events (morbidity) between the groups Compare lower limb lymphoedema between the groups Compare cost and cost effectiveness between the groups Determine the diagnostic accuracy of pre-operative, standardised high-resolution groin ultrasound to identify groin node metastasis. 
Translational research objective:
 
 To assess the role of blood and tissue molecular biomarkers to accurately determine the burden of disease (positive lymph nodes) in vulvar cancer, assist with risk stratification and aid disease surveillance |
| Study Endpoints | 
Primary endpoint:
 
 Incidence of clinically palpable, fixed to skin and histologically positive groin lymph nodes (node metastasis) at 12 months after surgical excision of the primary vulvar tumour |

| | |

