| 
Translational research
 | 
All participants (pending consent) will be asked to donate blood samples and Formalin-Fixed Paraffin Embedded (FFPE) tissue (vulvar tissue with/without lymph nodes) to be banked for the purpose of future molecular and biomarker research.
 
Tumour with/without groin lymph nodes will be collected at the diagnostic biopsy procedure and/or during surgery. Throughout the study, clinical trial coordinators at each site will arrange for blocks for each episode of biopsy or excision to be extracted (vulvar tissue, lymph nodes) and couriered to a central laboratory in QLD in batches as required and will undergo centralised histopathology review.
 
For participants who receive standard upfront groin LND, blood will be collected at two time points: prior to surgery (baseline) and 8 weeks post-surgery. For participants who have serial high-resolution groin USM, blood will be collected prior to surgery (baseline) and at each ultrasound scan (7-time points total). Blood samples will be processed and stored at local labs, and then couriered to a central laboratory in QLD in batches as required. Specimens will be stored for an indefinite period following the last participant completing the trial.
 
All translational research using these samples will be subject to a separate ethics application.
 |
| 
Study Design
 | 
A phase II, open label, domestic and international, three-group, randomised clinical trial.
 |
| 
Randomisation
 | 
Participants with a normal/negative baseline groin node ultrasound will be randomised 2:1 to receive radical wide local excision or radical vulvectomy with either:
 |

| | |

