| | 
 If the groin ultrasound is negative/normal (n=180), participants will be randomised 2:1 to receive either a groin LND (n=60) or bilateral groin USM every 2 months along with clinical examination every 3 months for a period of 12 months (n=120; no upfront groin LND). 
All participants will receive appropriate surgical excision of the primary tumour (radical wide local excision or radical vulvectomy). All lymph nodes will undergo central pathology review [1]. Postoperative treatment will follow local institutional treatment guidelines.
 |
| 
Stage details and number of participants
 | 
240 participants in total:
 
 Ultrasound negative/normal groin nodes (120 undergoing groin USM every 2 months along with clinical examination every 3 months and 60 upfront groin IFL/SNB) Ultrasound suspicious/indeterminate groin nodes (60 having upfront groin IFL/SNB) |
| 
Study Duration
 | 
Enrolment for this study is projected to conclude within a 4-year timeframe. The study will be deemed complete once 180 participants have been enrolled, randomised, and successfully completed a 12-month follow-up period.
 |

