5.6 Secondary Endpoint

1. HRQL and PROMS as measured by the EQ-5D and FACT-V at baseline, 8 weeks, 6 months, and 12 months
2. Morbidity at 12 months after surgery
3. Lower limb lymphoedema: incidence up to 12 months after surgery
4. Cost and cost effectiveness at 12 months post-surgery
5. Clinical accuracy of high-resolution ultrasound to predict groin lymph node involvement
6. Disease-free survival (DFS) and overall survival (OS)
7. Utility of biomarkers to reliably reflect the presence or absence of positive groin lymph nodes
8. Explore novel biomarkers for vulvar cancer

6. Study Design

A phase II, open label, multicentre, three-group, randomised clinical trial (ANVU).

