6.4 Randomisation

Eligible participants will be required to provide signed informed consent before being enrolled. Prior to enrolment, each patient will be screened for eligibility according to the inclusion and exclusion criteria. Participants will then receive a bilateral groin node ultrasound, participants who are found to have negative groin nodes will be randomised using a secure online randomisation system 2:1 to groin USM vs standard groin LND:

- ~120 participants will receive radical wide local excision or radical vulvectomy with serial high-resolution bilateral groin USM every 2 months in conjunction with clinical examinations every 3 months (groin lymph nodes are NOT removed).
- ~60 participants will receive radical wide local excision or radical vulvectomy with groin LND (Based on local clinical practice management guidelines.: either a SNB or an IFL).

Randomisation will be stratified by:

- Clinical stage
 - Depth of invasion (1-2 mm)
 - Depth of invasion (2.1-3 mm)
 - Depth of invasion 3.1 + mm
- HPV status
 - HPV positive
 - HPV negative
- Charlson Comorbidity Index ($<$ 5, \geq 5)

- Histological cell type
 - SCC
 - All other cell types (i.e. adenocarcinoma, melanoma).

Participants with a groin node ultrasound that is suspicious/indeterminate will not be randomised but receive standard groin LND (SNB or IFL as appropriate, as per institutional guidelines).

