11.2.9 Disease-Free and Overall Survival (DFS, OS)

Participants will be followed for 12 months and assessed for local, regional, or distant recurrence. Participants will be seen every 3 to 6 months. Clinical assessments will be performed at each visit. Clinical assessment, radiological work-up ± histological confirmation of recurrence will prove the presence of recurrent disease.

DFS is defined as time until the first recurrence or death from any cause. In patients without recurrence, or lost to follow-up, DFS will be censored on the date of the last follow-up visit. DFS will be compared between treatment arms using methods for the analysis of censored data. Variables to be evaluated for effect on DFS will include clinical management group (groin LND, ultrasound groin surveillance), age, medical comorbidities.

12 Trial Monitoring and Oversight

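### The cost-effectiveness objective compares all three groups, although one is non-randomised and selected on its ultrasound result; the DFS variable leaves the same question open

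*Protocol*

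**What the plan says.** The Synopsis describes "A phase II, open label, domestic and international, three-group, randomised clinical trial", and Section 6 repeats the three-group label. Section 6.4 makes clear that only two of the groups are randomised. Ultrasound-negative women are "randomised using a secure online randomisation system 2:1 to groin USM vs standard groin LND", whereas "Participants with a groin node ultrasound that is suspicious/indeterminate will not be randomised but receive standard groin LND". The planned sizes are 120 USM, 60 randomised LND and 60 non-randomised LND.

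On cost, Section 5.4 objective 4 reads "Compare cost and cost effectiveness between all groups". The Synopsis version of the same objective reads "Compare cost and cost effectiveness between the groups". Section 11.2.6 values resource use across the study groups, counts adjuvant treatment, and carries the result into a Markov model and an ICER. It does not name an analysis population.

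On DFS, Section 11.2.9 first says that DFS is compared by treatment arm. It then adds: "Variables to be evaluated for effect on DFS will include clinical management group (groin LND, ultrasound groin surveillance), age, medical comorbidities".

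Section 11.2 places all analyses under intention-to-treat and leaves estimands to the SAP. Among the between-group analyses, only the PROM comparison in Section 11.2.2 is expressly limited to the randomised groups.

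**The concern.** The third group is defined by a prognostic test result that no randomised woman shares. Setting USM against it compares women with a negative ultrasound to women with an abnormal one, and the difference in strategy cannot be separated from the difference in disease. Under Section 6.5.2, positive nodes can lead to radiation or further groin surgery, and Section 11.2.6 counts such treatment as cost. A group with more node-positive women will therefore tend to cost more whichever strategy is better. Because that group is managed by LND, the bias would probably make USM look cheaper than it is.

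Cost effectiveness is a stated aim of the trial (Section 5.2), so the comparison behind it should be the randomised one. The DFS variable raises a related question. Its label describes how women are managed rather than how they were allocated, and the non-randomised women are managed by groin LND.

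**Working it through.** **1. The plan's group sizes.** 180 × 2/3 = 120 USM and 180 × 1/3 = 60 LND; 180 + 60 = 240. These agree with the Synopsis. The non-randomised group is 60/240 = 25% of all women.

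**2. Does the cost objective include the third group?** Objectives 1 to 3 of Section 5.4, and the Synopsis version of the cost objective, refer to the groups without the word *all*; objective 4 adds it. Section 12.1 counts three groups when it describes safety monitoring, so the protocol does treat the suspicious/indeterminate women as a group. Section 11.2.6 does not narrow this. Read as written, the cost comparison includes them.

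**3. Does the DFS analysis include them?** The comparison is by treatment arm and intention-to-treat applies, which points to the two randomised arms. The two-level management variable does not say where the third group belongs, and baseline ultrasound result is not among the listed variables. The text permits pooling but does not state it.

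**4. Size, only if the two LND groups were pooled.** The non-randomised share of LND would be 60/(60 + 60) = 50%. For node positivity, let q_all be the overall prevalence and q_neg the rate after a negative ultrasound:

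- q_susp = (240 × q_all − 180 × q_neg)/60
- pooled LND = (60 × q_neg + 60 × q_susp)/120

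Inputs: q_all = 20% (Section 2), 30% (Section 3.2) or 32% (Section 11.1); q_neg = 3/32 = 9.4% (pilot, Section 3.4). Values of 5%, 15% and 20% for q_neg are assumptions.

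At 20% and 9.4%: 240 × 0.20 = 48; 180 × 3/32 = 16.9; 48 − 16.9 = 31.1; 31.1/60 = 52%. Pooled LND = (5.6 + 31.1)/120 = 31%, against 9.4% in USM.

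| q_all | q_neg | q_susp | pooled LND | ratio to USM |
|---|---|---|---|---|
| 20% | 20% | 20% | 20% | 1.0 |
| 20% | 15% | 35% | 25% | 1.7 |
| 32% | 20% | 68% | 44% | 2.2 |
| 20% | 9.4% | 52% | 31% | 3.3 |
| 30% | 9.4% | 92% | 51% | 5.4 |
| 32% | 9.4% | nearly 100% | 55% | 5.8 |

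The ratio is 1.0 only if ultrasound carries no information. With q_neg below the pilot value, at 5%, and q_all at 20%, it is 7.0.

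**5. What pooling could do to DFS.** All event rates here are assumed, with no true treatment effect. Take 12-month event rates of 40% (node-positive) and 10% (node-negative), with q_all 20% and q_neg 9.4%:

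- USM: 0.094 × 0.40 + 0.906 × 0.10 = 12.8%
- pooled LND: 0.306 × 0.40 + 0.694 × 0.10 = 19.2%
- apparent hazard ratio: ln(1 − 0.128)/ln(1 − 0.192) = 0.64

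With event-rate pairs 30%/10%, 40%/10% and 50%/5%, and q_all/q_neg of 20/9.4, 20/15, 30/15 and 32/20, the apparent hazard ratio runs from 0.43 to 0.86 and the spurious difference from about 2 to 14 percentage points.

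**6. Primary analysis.** The Section 11.1 safety criterion uses USM women only, so the third group cannot enter it. Under an assumed Beta(1.5, 31.5) prior, the stated stopping boundaries reproduce exactly, with 0.847 probability of declaring safety (stated 0.85) and 0.018 of stopping wrongly (stated below 2%).

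**The case against.** Read literally, objective 4 keeps three groups apart, so the randomised USM–LND contrast survives beside the others. Section 11.2.6 is also aimed at the cost of each intervention and an ICER, and never specifies a direct contrast of USM with the suspicious group. That limits the harm but does not remove the point: the objective still calls for comparisons with a group selected on prognosis, and nothing says which contrast feeds the ICER.

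It can also be said that intention-to-treat settles the matter and that analysis populations belong in the SAP. Intention-to-treat is not a blanket restriction to the 180 randomised women, because it also heads Section 11.2.5, which takes in every woman receiving groin LND. The SAP argument is fair where the protocol is silent, but objective 4 is a positive statement that differs from its own Synopsis.

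A reader might go further and infer that the protocol pools all LND women for DFS, or that the morbidity and lymphoedema comparisons are confounded too. The document does not support this. Section 11.2.9 compares treatment arms and nowhere assigns the third group to the LND level. The silence of Sections 11.2.3 and 11.2.4 on population is a detail a SAP can settle. The three-group label alone is not an error, since the protocol states openly that the third group is not randomised.

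The objection to the node-positivity figures largely stands. They combine positives found by surveillance (3/32, 95% Wilson interval about 3% to 24%) with histological prevalence. The top of the range would make almost every suspicious or indeterminate scan node-positive, which is an arithmetic bound and not a forecast.

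**Conclusion.** The point holds for cost and cost effectiveness: as written, the comparison includes about 60 non-randomised women, and any contrast of USM with them is confounded by the baseline ultrasound result. The likely direction favours USM, provided that an abnormal ultrasound goes with more node-positive disease. The size in dollars or QALYs cannot be derived from the protocol. For DFS it is an ambiguity to close, not a stated error.

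The imbalance of about 31% against 9.4% node-positive is conditional on pooling, which no section orders, and on the pilot rate carrying over to this trial. The DFS hazard ratios rest on assumed event rates as well. The stopping rule is untouched, as are the primary endpoint and sample size.

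**What to change.** - Section 5.4 objective 4 and Section 11.2.6: state that the incremental cost, QALY and ICER comparison is *between the randomised groups (USM vs LND, by allocation)*. Carry the same words into the Synopsis objective so that the two agree.
- Section 11.2.9: replace *clinical management group* with *randomised arm*.
- Report the suspicious/indeterminate cohort separately and descriptively, including its costs and DFS if wanted, and keep it in the ultrasound accuracy analysis of Section 11.2.5.

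The cost is wording only. Data collection, sample size and the primary analysis do not change.
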